4.5 Safety Analysis

4.5.1 General Considerations

Analysis population

Safety population will be used for safety analyses of AEs, clinical laboratory data, Columbia Suicide Severity Rating Scale (C-SSRS) data, ECG data and vital sign data (all the safety data except for ARIA data). Safety MRI population will be used for analyses of ARIA data.

Final V1.0

Safety treatment groups

Different from the randomization treatment groups, if a subject who was randomized to placebo group accidentally received one or more doses of the active treatment during the study, he/she will be classified as either low or high dose group for all the safety analyses, depending on the ApoE status and the maximal dose level of the active treatment received (Table 5). A listing of such subjects will be provided, as described in section 4.2.5. Safety treatment groups will be the same as the randomization treatment groups for other subjects (subjects randomized to active treatment groups, and subjects randomized to placebo without any accidental active dose). Safety treatment groups will be used for all the safety analyses unless otherwise specified.

Table 5: Safety treatment groups for placebo subjects with accidental active treatment

Randomization treatment group	Randomization ApoE status	Safety treatment group classification based on the maximum dose level of the accidental active treatment		
		>0 to 3 mg/kg	>3 to 6 mg/kg	>6 mg/kg
Placebo	ΑροΕ ε4 (+)	Low dose	High dose	High dose
	ΑροΕ ε4 (-)	Low dose	Low dose	High dose

Safety analysis displays

AEs, clinical laboratory data, C-SSRS data, ECG data and vital sign data (all the safety data except for ARIA data) will be summarized by treatment group (placebo, low dose, high dose and BIIB037 total; analysis display A in Appendix 6.1), unless otherwise specified. All the ARIA related tables will be presented by treatment group stratified by ApoE status (3 columns under each treatment group: ApoE ϵ 4+, ApoE ϵ 4- and total; analysis display B in Appendix 6.1), unless otherwise specified. A subset of AE tables will also be presented by treatment group stratified by ApoE status in addition to by treatment group. All the listings will be presented by treatment group stratified by ApoE status.

Incidence, incidence proportion and incidence rate

Incidence and incidence proportion will be provided in incidence tables. Incidence is
defined as the number of subjects who experienced an event. Incidence proportion is

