4.5.3.5 Time to event analysis

Kaplan-Meier plot of time to first ARIA-E event will be produced based on safety MRI data. Time to event is calculated as date of the MRI assessment that initially detects ARIA-E event - date of first infusion (aducanumab or placebo) +1. Censor time for subjects without ARIA-E is calculated as date of last MRI assessment in the placebo-controlled period - date of first infusion (aducanumab or placebo) +1. Estimated proportion with ARIA-E and number of subjects at risk at selected timepoints will also be presented. The plot will be presented by treatment group stratified by ApoE status.

4.5.3.6 Subgroup analysis for protocol version 4

Due to the change in maximal dose from 6 mg/kg to 10 mg/kg for ApoE &4 carrier high dose group in protocol version 4, not all subjects have had opportunity to receive the protocol specified high dose (6 doses in titration before receive 10mg/kg) in the placebo-controlled period. Incidence of ARIA events and summary of first ARIA-E events tables will be provided for ApoE &4 carriers who were randomized to the high dose group, stratified by the expected number of doses at 10 mg/kg (categories of 0, 1-6, 7-13, 14, and a total column of having at least one dose) a subject would have received based on the first infusion date and the date consenting to protocol version 4. Randomization treatment groups will be used for this analysis.

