Informed Consent	Subject/informant/legally authorized representative did not sign Main ICF, PET ICF, and/or Substudy ICFs (and substudy procedures were conducted). Not clear on the ICF who has been signing the document (patient or legal representative).	Major
Informed Consent	Principal Investigator / individual obtaining consent did not sign Main ICF, PET ICF, and/or Substudy ICFs (and substudy procedures were conducted).	Major
Informed Consent	Not clear on the the ICF who has been signing the document (patient or legally authorized representative).	Major
Informed Consent	ICF signed by either only patient or only care giver/legally authorized representative, when ICF should have been signed by both.	Major
Informed Consent	Incorrect or outdated version of Main ICF, PET ICF, and/or Substudy ICFs signed by subject/informant/legally authorized representative.	Major
Informed Consent	IEC/IRB contact details or site's contact details not included on ICF.	Minor
Informed Consent	Incorrect completion of ICF (i.e., subject/study partner/LAR/person obtaining consent did not provide date of signature; subject/study partner/LAR/person obtaining consent noted incorrect date of signature; subject/study partner/LAR/person obtaining consent printed name when should have signed, subject/study partner/LAR/person obtaining consent signed on line for printed name, printed name on line for signature, etc.)	Minor
Informed Consent	Site personnel who signed ICF is not on Site Personnel Signature Delegation Log and/or not authorized by PI to sign ICF	Major
Informed Consent	No evidence (source documentation) that Informed Consent was obtained from the study subject / study partner.	Major
Informed Consent	ICF obtained by subject is not in subject's native language.	Major
Informed Consent	Protocol specific procedures such as physical exam, medical history, neurological history, ECGs, rater scales, lab tests, blood draws, including first study drug dose performed prior to the date of the consent.	Major
Informed Consent	Subject and/or Study Partner/Caregiver not signing ICFs at time of reconsent.	Major
Informed Consent	Untimely reconsenting of subject/caregiver on newly approved ICFs.	Major
Investigational Product Compliance	IP storage temperature out of range and site used IP without confirmation from Biogen regarding usability	Case by case basis
Investigational Product Compliance	Incorrect cohort IP dispensed to subject	Major

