For amyloid PET by visit summaries and MMRM models, the analysis visit should be defined using visit windows (see Table 4 below). The rationale is to use the same analysis visit windows as for the efficacy endpoints for the visits that the efficacy endpoints are also collected. Since the visit for the efficacy measurements is on Week 134, while the visit for amyloid PET measurements is on Week 132, the start of the analysis visit window for Week 132 amyloid PET is 2 weeks earlier than that for efficacy, while the same end of the analysis visit window as Week 134 is used to be conservative. If there is more than 1 value in the same analysis visit window (>1 value for the same analysis visit) for a certain parameter for a subject, then the closest record to the target visit day will be used for the by visit analysis. If they are with the same distance from the target visit day, then the record with the later time will be used for the by visit analysis.

Table 4. Visit Windows for amyloid PET data

Analysis visit *	Target visit day	Analysis visit window	
Baseline	1	Most recent non-missing pre-dose value	
Week 26	183	[92, 266]	
Week 78	547	[449, the end day of the placebo-controlled period ¹]	
Week 132	925	[827, 1036]	
Week 182	1275	[1205, 1365]	
Week 260	1821	[1731, 1911]	
Week 338	2367	≥ 2277	

Analysis visit is the visit at which the specific week started.

3.5 **Safety Analyses**

General Considerations

Analysis population

Safety population will be used for safety analyses of AEs, clinical laboratory data, Columbia Suicide Severity Rating Scale (C-SSRS) data, ECG data and vital sign data (all the safety data except for ARIA data). Safety MRI population will be used for analyses of ARIA data.

LTE safety treatment groups

Since all the subjects are supposed to receive active treatment in LTE, the LTE safety treatment groups which are exactly the same as the LTE randomization treatment groups will be used for all the safety analyses. Subjects who were randomized to placebo group but accidentally received one or more doses of the active treatment during the placebo-controlled period will still be classified as late start for all the safety analyses that involves LTE, but their applicable safety data in the placebo-controlled period will be included in the analysis for placebo-controlled and LTE active treatment period.

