- 9. AEs by maximum severity by system organ class and preferred term (by LTE treatment group) (System organ class will be presented alphabetically. Preferred terms will be presented in decreasing frequency order. Maximum severity will be presented within each preferred term in the order of mild, moderate, severe, unknown and total.

Final V1.0

A subject will be counted only once at the maximum severity within each system organ class and preferred term.)

- 10. AEs by maximum severity by preferred term (by LTE treatment group) (Preferred terms will be presented in decreasing frequency order. Maximum severity will be presented within each preferred term in the order of mild, moderate, severe, unknown and total. A subject will be counted only once at the maximum severity within each preferred term.)
- 11. Related AEs by system organ class and preferred term
- 12. SAEs by system organ class and preferred term
- 13. SAEs by preferred term
- 14. Related SAEs by system organ class and preferred term
- 15. AEs that led to discontinuation of study treatment by system organ class and preferred term
- 16. AEs that led to withdrawal from study by system organ class and preferred term
- 17. SAEs with fatal outcome by system organ class and preferred term
- 18. AEs that occurred within 2 hours from infusion start by system organ class and preferred term (by LTE treatment group)

The following listings will be provided for the placebo-controlled and LTE period:

- 1. Listing of AEs
- 2. Listing of SAEs
- 3. Listing of AEs that led to discontinuation of study treatment
- 4. Listing of AEs that led to withdrawal from study
- 5. Listing of AEs that occurred within 2 hours from infusion start
- 6. Listing of AEs related to PET ligands
- 7. Listing of SAEs with fatal outcome
- 8. Listing of AEs for subjects with treatment-emergent positive anti-BIIB037 antibody

3.5.2.2 Incidence and incidence rate analysis for placebo-controlled and LTE active treatment period

Due to the different length of placebo-controlled and LTE active treatment period in early start versus late start subjects, both incidence tables and follow-up adjusted incidence rate tables will be used for AE analyses in this period. The entire follow-up time is from the first dose in active treatment period (first dose in placebo-controlled period for early start subjects and first dose in LTE period for late start subjects) until the last day in the study.

Final V1.0

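### The LTE SAP admits placebo-period safety events from misdosed placebo subjects but starts their follow-up time at the first LTE dose

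*SAP*

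**What the plan says.** **Placebo-controlled SAP, 4.5.1.** A placebo subject who "accidentally received one or more doses of the active treatment during the study, he/she will be classified as either low or high dose group" is placed in low or high dose by ApoE status and highest accidental dose (Table 5). For everyone else, "Safety treatment groups will be the same as the randomization treatment groups for other subjects". In 4.5.3.4 the ARIA-E exposure-adjusted time starts at the first dose. In 4.5.3.5 the Kaplan-Meier time is counted from the "date of first infusion (aducanumab or placebo) +1".

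**LTE SAP, 3.5.1 (LTE safety treatment groups).** The same subjects "will still be classified as late start for all the safety analyses that involves LTE". The sentence goes on to admit their *applicable* placebo-period safety data to the analysis of the combined active-treatment period. It does not say which data are applicable.

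**LTE SAP, 3.1.2.** That period is defined by assignment. Early start subjects contribute both periods, and late start subjects contribute LTE data only.

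**LTE SAP, 3.5.1 (LTE baseline).** Late start subjects take their baseline, study day and visit windows from the first LTE dose.

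**LTE SAP, 3.5.2.2.** Follow-up time in this period begins at the "first dose in LTE period for late start subjects".

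**The concern.** A follow-up-adjusted rate is only meaningful if each counted event falls inside the time in its denominator. For a misdosed placebo subject, one sentence of the LTE SAP opens the numerator to placebo-period events and another closes the denominator until the first LTE dose. A third excludes the same data altogether. A programmer cannot follow all three, and the choice would be made after the data are known. The outputs at stake are the integrated AE rate tables (3.5.2.2), the follow-up-adjusted rates of one or more ARIA-E events (3.5.3.3), and the baseline and visit windows for laboratory, vital-sign and immunogenicity data.

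A smaller matter concerns the placebo-controlled SAP. A reclassified subject sits in an active column, but the ARIA-E clock starts at a placebo infusion, so onset relative to drug is dated too late.

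**Working it through.** There is no stated figure to reproduce. The check sets the rules side by side and then sizes the gap.

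**1. Rules for a misdosed placebo subject in the LTE SAP**

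| Place | Rule |
|---|---|
| 3.1.2 | Late start: LTE data only |
| 3.5.1, treatment groups | Late start, with applicable placebo-period data included |
| 3.5.1, LTE baseline | Baseline and study day from first LTE dose |
| 3.5.2.2 | Follow-up from first LTE dose |
| 3.5.3.3, follow-up-adjusted rate | Entire follow-up in the active-treatment period; no separate start given |
| 3.5.3.3, time to first ARIA-E | From first active infusion |
| 3.5.3.4 and 3.5.3.5 | From first active dose or infusion |
| Tables 5, 6 and 7 | Windows and baseline from first aducanumab dose, with a column for each period in which it was received |

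The last three rows already use first actual exposure. The conflict lies among the first five, and between the LTE-baseline rule and Tables 5 to 7.

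**2. An example.** The first accidental active dose is infusion 10 and an AE starts at Week 50.
- Infusion *k* falls at week 4(*k* − 1), so infusion 10 is at Week 36.
- The first LTE dose is at about Week 80: 76 weeks of treatment plus 4 weeks of follow-up. LTE SAP 3.5.3.2 also calls Week 80 the first LTE visit.
- 3.1.2 excludes the AE. 3.5.1 admits it, if *applicable* means after first exposure.
- Under 3.5.2.2 the clock starts at Week 80, so the AE lies 80 − 50 = 30 weeks before time zero. The 80 − 36 = 44 weeks in which it could arise are not in the denominator.
- If the subject never enters the LTE, there is no first LTE dose and no follow-up time is defined, although 3.5.1 still admits the event.

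**3. Missing person-time per subject:** 80 − 4(*k* − 1) weeks.

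| First active infusion *k* | 1 | 5 | 10 | 15 | 20 |
|---|---|---|---|---|---|
| Weeks missing | 80 | 64 | 44 | 24 | 4 |

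If *k* is equally likely to be 1 to 20 (assumed), the mean of 4(*k* − 1) is 38, so 80 − 38 = 42 weeks are missing on average.

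**4. Size in one late start group.** Placebo has 535 planned subjects, split 1:1, so about 267 per late start group if all enter the LTE (an upper limit). Full LTE follow-up is 256 + 18 = 274 weeks; 52 weeks is an assumed short alternative. Affected subjects: 1 to 10 (assumed), all in one group.
- Full follow-up: 267 × 274 = 73,158 person-weeks. Missing: 42/73,158 = 0.06% to 420/73,158 = 0.57%.
- Short follow-up: 267 × 52 = 13,884 person-weeks. Missing: 42/13,884 = 0.30% to 420/13,884 = 3.0%.
- If *applicable* meant the whole placebo period, 80 weeks are missing per subject. For 10 subjects: 800/73,158 = 1.1% to 800/13,884 = 5.8%.
- One added subject with an event is 1/267 = 0.37 percentage points of the group.

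**5. ARIA-E time in the placebo-controlled SAP.** Time from first infusion overstates time from first active infusion by 4(*k* − 1) weeks: 0, 16, 36, 56 and 76 weeks for *k* = 1, 5, 10, 15 and 20, with mean 38 under the same assumption.

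**The case against.** The strongest reply is that most of this is already handled. The LTE SAP times first ARIA-E onset, the exposure-adjusted ARIA-E rate and the Kaplan-Meier plot from first active exposure, and sets its laboratory, vital-sign and immunogenicity windows from the first aducanumab dose. Calling these subjects late start has a stated reason: everyone is meant to receive active drug in the LTE. *Applicable* was probably meant as data after first exposure. All of this stands, and it narrows the point to 3.1.2, the two parts of 3.5.1, 3.5.2.2 and the follow-up-adjusted rates in 3.5.3.3. It does not remove the mismatch there.

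A reader might infer more: that Table 5 is itself wrong because it moves a placebo subject's whole record to an active column, while a low-dose subject given a higher dose stays in low dose. The asymmetry is in the text, but the documents do not make it an error.
- The rule is explicit and pre-specified. Keeping any exposed subject out of the placebo column, and actively randomized subjects in their arm, is a coherent choice.
- "Incorrect cohort IP dispensed to subject" is a generic Major deviation in 6.2. It does not show that low-dose subjects receive high-dose product.
- Section 4.2.5 lists every dose and summarizes the maximum dose by arm and ApoE status. For ARIA-E subjects, 4.5.3.3 gives the last dose level before a first event, and 4.5.3.4 counts prior infusions at each level, placebo included. Misdosing would be visible.
- Extending the maximum-dose rule to low-dose subjects would move whole records again. Splitting subjects would put one person in two incidence denominators and raise the question of which baseline applies.
- The numerical effect is small. With 535 per arm and 10 moved subjects who keep an assumed 3% risk in a high-dose arm at 35%, the rate is (535 × 0.35 + 10 × 0.03)/545 = 34.41%, a fall of 0.59 points. Ten low-dose subjects with an assumed 35% risk in an arm at 25% give (525 × 0.25 + 10 × 0.35)/535 = 25.19%, a rise of 0.19 points.

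**Conclusion.** The point holds for the LTE SAP, at minor severity. For placebo subjects with accidental active dosing, 3.1.2, 3.5.1 and 3.5.2.2 give incompatible rules on which data enter and when time begins. The follow-up-adjusted AE and ARIA-E rates can therefore count events with no matching person-time. It would be wrong to conclude that all integrated rates for these subjects lack a denominator, because the exposure-adjusted ARIA-E and Kaplan-Meier analyses do not.

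The missing time is about 42 weeks per affected subject if errors are spread evenly over the infusions, and between 4 and 80 weeks in any one case. For 1 to 10 subjects in one late start group this is about 0.06% to 3% of follow-up. The number of subjects, the timing of errors and the 52-week alternative are assumptions; the documents give none of them.

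In the placebo-controlled SAP only the ARIA-E time origin and the labelling of pre-exposure events need attention. The Table 5 classification can stay.

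**What to change.** **LTE SAP.** In 3.1.2, 3.5.1 and 3.5.2.2, state that for placebo subjects with accidental active dosing the active-treatment period, the applicable data, the baseline and the follow-up time all start at the first actual aducanumab infusion, including for those who never enter the LTE. Refer 3.5.3.3 to the same start. This agrees with 3.5.3.4, 3.5.3.5 and Tables 5 to 7. The late start label can remain.

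**Placebo-controlled SAP.** Keep Table 5. For reclassified placebo subjects, start ARIA-E time in 4.5.3.4 and 4.5.3.5 at the first active infusion. Flag in a footnote or listing any AE or ARIA event that began before it. Say how an ARIA-E event with earlier onset is treated in those two analyses, since it has no valid time on the new scale.

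**Cost.** A few sentences and one derived date, taken from dosing records that both SAPs already list. No new data are needed and no subject changes column.

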defined as the number of subjects who experienced an event divided by total number of
subjects in the analysis population, i.e., percentage. Each subject will be counted only
once within each category.

Final V1.0

- Incidence and incidence rate will be provided in incidence rate tables. Two different kinds of incidence rate tables will be provided as appropriate for different analyses. Definitions are provided below.
 - (1) Follow-up adjusted incidence rate defined as the number of subjects who experienced an event divided by the total of entire follow-up time among the subjects in the analysis population. The entire follow-up time for a subject is defined as the time from the first dose until the last day on study. Each subject will be counted only once within each category.
 - (2) Exposure-adjusted incidence rate (EAIR) defined as the number of subjects who experience an event divided by the total exposure adjusted follow-up time among the subjects in the analysis population. The exposure adjusted follow-up time is defined as the time from the first dose until the initial occurrence of the event for those who experienced an event, or from the first dose until the end of follow-up (the last day on study) for those who did not. Each subject will be counted only once within each category.

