4.5.2 Clinical Adverse Events

Treatment-emergent AEs (TEAEs)

All AEs will be analyzed based on the principle of treatment emergence. A treatment-emergent AE was defined as an AE that started or worsened after the start of first infusion of study treatment.

To define treatment emergence for AEs with missing start or stop date or time the following additional criteria will be used:

- if both the start and stop dates for a particular AE are missing, then that AE is considered treatment emergent;
- if the start date for a particular AE is missing and the stop date/time falls after the first dose date/time, then that AE is considered treatment emergent;
- if the start date for a particular AE was the same as the first dose date, and the start time was missing, then that event is considered treatment emergent.

For AEs with a partial start date, the year/month of the event date will be compared to that of the first dosing date to determine whether the event is treatment emergent.

In addition, SAEs that occurred since a subject was screened in the study and prior to the first infusion of study treatment, which by definition are not treatment-emergent, will be analyzed separately.

Only TEAEs will be included in the AE tables, unless otherwise specified. Listings of AEs will include all events, whether treatment-emergent or not.

As specified in the protocol, subjects were expected to return to the study site for an End of Study visit 18 weeks after the last administration of study treatment. However, some subjects may elect to continue study participation on a modified schedule after discontinuing treatment, possibly in substantial excess of 18 weeks. For most general AE summaries, AEs

Final V1.0

with an onset more than 18 weeks after the last dose will be excluded (will specify in the footnote of the specific table). For incidence rate analyses excluding AEs more than 18 weeks after the last dose, the "last day on study" in follow-up time calculation will be replaced with "18 weeks after last dose or last day on study, whichever earlier". Summaries of deaths and AEs leading to study withdrawal, and other selected analyses will include all AEs regardless of the time since the last dose. Listings will include all AEs, unless otherwise specified.

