4.5.2.2 Incidence rate analysis

Follow-up adjusted incidence rate for the placebo-controlled period will be summarized by system organ class and preferred terms both by treatment group and by treatment group stratified by ApoE status.

Final V1.0

4.5.2.3 Subgroup analysis for protocol version 4

Due to the change in maximal dose from 6 mg/kg to 10 mg/kg for ApoE &4 carrier high dose group in protocol version 4, not all subjects have had opportunity to receive the protocol specified high dose (6 doses in titration before receive 10mg/kg) in the placebo-controlled period. Incidence tables of AEs and SAEs will be provided for ApoE &4 carriers who were randomized to the high dose group, stratified by the expected number of doses at 10 mg/kg (categories of 0, 1-6, 7-13, 14, and a total column of having at least one dose) a subject would have received based on the first infusion date and the date consenting to protocol version 4. Randomization treatment groups will be used for this analysis.

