4.5.3.3 Summary of recurrent ARIA-E

Follow-up adjusted incidence rate of subjects with ARIA-E, with 2 or more events of ARIA-E, with 3 or more events of ARIA-E and with more than 3 events of ARIA-E based on their entire follow-up time will be summarized based on AE eCRF. The entire follow-up time is from the first dose until the last day in the placebo-controlled period.

Number of total ARIA-E events and the MRI severity of each event will be summarized based on AE eCRF. Number of total symptomatic ARIA-E events, the MRI severity of each symptomatic event and the severity of the symptoms of each symptomatic event will be summarized based on AE eCRF.

Summary of first ARIA-E events table based on AE eCRF will summarize the number of subjects with a first event of ARIA-E, the MRI severity of the events, the symptomatic status of the events, the severity of the symptoms for symptomatic events, whether SAE or not, number of resolved and unresolved events, duration of the resolved events, time from first infusion in study (active or placebo) to onset, number of doses received since the start of the study to onset, dose level of the last infusion received prior to onset, dosing status (continue as planned, dose interrupted, dose reduced, or dose discontinued) after the events, and the number of subjects with recurrent ARIA-E events. The same summary of first ARIA-E events table will also be done on subjects who had recurrent ARIA-E events.

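### The only incidence rate planned for general AEs counts each subject once but keeps person-time after the event in the denominator, so it is too low as a first-event rate for common events

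*SAP*

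**What the plan says.** Section 4.5.1 of the placebo-controlled SAP defines two rates with the same numerator: "Each subject will be counted only once within each category".

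- **Rate (1), follow-up adjusted.** The count is "divided by the total of entire follow-up time among the subjects in the analysis population". The person-time rule is "The entire follow-up time for a subject is defined as the time from the first dose until the last day on study", whether or not the subject had the event.
- **Rate (2), EAIR.** Person-time runs "from the first dose until the initial occurrence of the event for those who experienced an event", and to the end of follow-up for the others.

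For general AEs, Section 4.5.2.2 names only rate (1): "Follow-up adjusted incidence rate for the placebo-controlled period will be summarized by" organ class and term. LTE SAP Section 3.5.2.2 points to the unequal lengths of the early-start and late-start active periods and says that "both incidence tables and follow-up adjusted incidence rate tables will be used for AE analyses in this period".

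The EAIR is planned only for ARIA-E on MRI data (Section 4.5.3.4; LTE SAP Section 3.5.3.4). Section 4.5.3.3 also uses rate (1) for subjects with ARIA-E, "based on their entire follow-up time will be summarized based on AE eCRF". Where late AEs are excluded, Section 4.5.2 ends follow-up at "18 weeks after last dose or last day on study, whichever earlier". That moves the end of follow-up but does not stop the clock at the event.

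**The concern.** A subject who has had a first event is no longer at risk of one. Leaving that subject's later time in the denominator of a first-event count lowers the rate, and more so the commoner and earlier the event. The SAP gives no reason for preferring rate (1) over rate (2) for general AEs.

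Two readings are at stake. In the placebo-controlled period, a reader who takes the tabulated figure as events per person-year at risk will take too low a figure for common AEs. In the LTE, the rate is brought in because period lengths differ, yet subjects who had the event keep adding time, and the longer-followed early-start groups have more of it to add.

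**Working it through.** The SAP states no AE rate, so there is no figure to reproduce. Both definitions were applied to the same assumed data.

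**Inputs from the SAP.** Section 2.1 gives a 76-week treatment period, 18 weeks of safety follow-up, a 256-week LTE treatment period and 362 weeks in total including 8 weeks of screening. Section 3 gives 30% drop-out.

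**Assumptions.** The documents give no AE frequency or timing. Taken here: p from 1% to 35%; mean onset at f = 0.10, 0.25 or 0.50 of follow-up, or a constant hazard.

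**Formulas, equal follow-up T.**
- Rate (1) = p/T.
- EAIR = p/[T(1 - p + fp)], so rate (1)/EAIR = 1 - p(1-f) and the shortfall is p(1-f).
- Under constant hazard, EAIR = -ln(1-p)/T and the shortfall is 1 - p/[-ln(1-p)].

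The shortfall does not depend on T.

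**Example.** p = 20%, T = 78 weeks (1.495 years), f = 0.25. Rate (1) = 0.20/1.495 = 13.38 per 100 person-years. EAIR = 0.20/(1.495 × 0.85) = 15.74. Shortfall = 0.20 × 0.75 = 15%.

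| p | constant hazard | f = 0.50 | f = 0.25 | f = 0.10 |
|---|---|---|---|---|
| 1% | 0.5% | 0.5% | 0.8% | 0.9% |
| 5% | 2.5% | 2.5% | 3.8% | 4.5% |
| 20% | 10.4% | 10.0% | 15.0% | 18.0% |
| 35% | 18.8% | 17.5% | 26.2% | 31.5% |

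**Drop-out check.** A simulation of 1,000,000 subjects with 30% drop-out gives similar shortfalls at p = 5%, 20% and 35%: 2.4%, 9.8% and 17.8% under constant hazard, and 3.6%, 14.4% and 25.2% with onsets spread over the first half of the period.

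**LTE, constant hazard.** Maximum early-start follow-up is 362 - 8 = 354 weeks; maximum late-start follow-up is 256 + 18 = 274 weeks. With the same hazard in both, p(early) = 1 - [1 - p(late)]^(354/274), and the early/late ratio of rate (1) is [p(early)/354]/[p(late)/274].

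| p(late) | p(early) | rate (1) ratio | EAIR ratio |
|---|---|---|---|
| 20% | 25.0% | 0.97 | 1.00 |
| 35% | 42.7% | 0.94 | 1.00 |
| 50% | 59.2% | 0.92 | 1.00 |

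**LTE, front-loaded onset.** Suppose 20% of both groups have the event, all at 0.4 years (20.9 weeks).
- Rate (1) ratio: 274/354 = 0.774.
- EAIR ratio: (0.8 × 274 + 0.2 × 20.9)/(0.8 × 354 + 0.2 × 20.9) = 223.4/287.4 = 0.777.
- At 40%, the EAIR ratio is 172.8/220.8 = 0.783.

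Nearly all of this dilution comes from subjects without the event, whose long follow-up both rates count.

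**The case against.** The strongest defence is that rate (1) is a declared choice. Section 4.5.1 names and defines it openly, and nothing in the SAP contradicts it. No test, threshold or screening rule uses it: the AE tables in Section 4.5.2.1 that select on a 2% excess or on 5% frequency work on incidence. The same section tabulates AEs by 12-week interval, so timing is visible, and ARIA-E has an EAIR and a Kaplan-Meier plot. All of this stands, and it limits the point to the rate tables.

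A reader might infer that rate (1) biases the active-placebo contrast. The documents do not support that. With equal follow-up, the ratio of two such rates is the risk ratio, a valid measure. For assumed proportions of 35% and 10%, it is 3.50 against an EAIR ratio of 4.09 under constant hazard. These are different measures, and the gap between them is not bias.

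A reader might also call the EAIR the correct rate. It summarises a hazard well only when the hazard is roughly constant, and the LTE calculation shows that it does little when onset is early. Nor does rate (1) adjust for nothing: it does respond to unequal drop-out between arms.

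**Conclusion.** The point holds as a mismatch between numerator and denominator in the general AE rate tables of both SAPs. As a first-event rate, rate (1) falls short by about p(1-f): at most 1% at p = 1%, 2.5-4.5% at 5%, 10-18% at 20% and 18-32% at 35%. In the LTE, for late-start incidence of 20% to 50%, it shows the early-start groups 3-8% lower than the late-start groups when the hazard is the same and constant.

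These sizes rest on assumed frequencies and onsets, and the LTE figures also on maximum durations. It would go too far to conclude that the safety report as a whole understates common early events: subject counts and proportions are reported in full. It would equally go too far to expect the EAIR alone to settle the early/late comparison. This is a modest improvement to how rates are presented and does not touch efficacy.

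**What to change.** In Section 4.5.2.2 and LTE SAP Section 3.5.2.2, present the EAIR that Section 4.5.1 already defines, either in place of the follow-up adjusted rate or beside it. State that the 18-week cut-off in Section 4.5.2 also sets the end of follow-up for the EAIR where late AEs are excluded. If rate (1) is kept, add a footnote saying that its denominator includes time after the event.

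For the LTE active-treatment tables, also show early versus late start over an equal time since first active dose, because neither rate deals with front-loaded onset over unequal periods.

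The cost is a change of SAP wording, reuse of the EAIR program planned for ARIA-E and a few more tables. No new data are needed.
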